11.4 Populations for Analysis

11.4.1 Safety population

All patients will be evaluable for toxicity from the time of their first treatment with Neoral and throughout the study period. In this study, patients will receive 7 days of Neoral and incidence of Neoral-associated toxicity events (see 11.5) and all AEs will be assessed daily.

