1.2 Secondary Objectives

- 1.2.1 To establish the safety of Neoral in this patient population (adverse events).
- 1.2.2 To determine the effect of Neoral on serum inflammatory markers (CRP, d-dimer, ferritin, ANC, absolute lymphocyte count, WBC, PLT (daily while inpatient and including day 14 and 28 for those discharged).
- 1.2.3 To determine the effect Neoral on viral SARS-CoV2 PCR positivity from baseline (day 0 to -2) before receiving Neoral) to day 14, and from baseline to day 28.
- 1.2.4 To determine the effect of Neoral on survival (days 14 and 28)
- 1.2.5 To determine the effect of Neoral on disease improvement (alive and free of invasive or non-invasive mechanical ventilation; days 14 and 28).
- 1.2.6 To determine the effect of Neoral on proportion of those requiring invasive mechanical ventilation.
- 1.2.7 To determine the effect of Neoral on incidence of deep vein thrombosis.
- 1.2.8 To determine the effect of Neoral on proportion of patients discharged on day 28.
- 1.2.9 To determine the effect of Neoral on time to hospital discharge.
- 1.2.10 To determine the effect of Neoral on disease resolution (alive and discharged home without oxygen; days 14 and 28).

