6. TREATMENT AND/OR IMAGING PLAN

6.1 Agent Administration

Treatment will be administered on an inpatient basis. Reported adverse events and potential risks are described in Section 10. Appropriate dose modifications are described in Section 7

Arm A Regimen Description					
Agent	Premedications; Precautions	Dose	Route	Schedule	Cycle Length
Neoral, Investigational, Generic Acceptable,	NA	2.5 mg/kg	PO	BID	7 days

N=50 Patients					

Arm B Regimen Description					
Agent	Premedications; Precautions	Dose	Route	Schedule	Cycle Length
None*, N= 25 Patients	NA	NA	NA	NA	7 days

*Note: The PI has undertaken thorough discussions with the sponsor and generation of placebo capsules is not feasible for the timing of this study.

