6.4 Duration of Follow-Up

Patients will be followed for 60 days after beginning the 7. day course of neoral or until death, whichever occurs first. Please refer to the schedule of events (**Table 1**), below. Patients experiencing adverse event(s) that require cessation of Neoral will be followed until resolution or stabilization of the adverse event.

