11.5 Analysis of Secondary Endpoints

The secondary objectives are mostly concerned with the safety and effects of Neoral (CSA) in this patient population. The secondary endpoints include Neoral-associated toxicity events, serum inflammatory markers (CRP, d-dimer, ferritin, ANC, absolute lymphocyte count, WBC, PLT (daily while inpatient and including day 14 and 28 for those discharged), Viral load (days 14 and 28), vital status (days 14 and 28), disease improvement (days 14 and 28), proportion of those requiring invasive mechanical ventilation, incidence of deep vein thrombosis, proportion of patients discharged on day 28, time to hospital discharge, and disease resolution (days 14 and 28).

For safety, Neoral-associated toxicity events include nephrotoxicity, resistant hypertension, hepatotoxicity, signs of CNS toxicity, or superinfection. AE's and SAE's by CTCAE v5 will be summarized descriptively with frequencies and rates. Rates and 95% CI's of grade 3 and above AE's will be reported.

Serum inflammatory markers are viewed as interval scales and after appropriate normalizing transformation (if needed), will be analyzed using general linear mixed models to account for within patient dependencies to allow comparisons between groups.

Viral positivity between groups at days 14 and days 28 will be tested by Wilcoxon rank sum test.

Survival analysis methods will be used to describe overall survival experience, to estimate survival at selected time points, and to compare groups. Cumulative incidence analysis methods will be used if there are competing risks. The same approach will be used with disease improvement (alive and free invasive or non-invasive mechanical ventilation) and disease resolution (alive and discharged home without oxygen).

Fisher's exact test will be used to compare rates of need for invasive mechanical ventilation bench marked to a particular time, and ever need. If required, this endpoint will include deaths before intubation in the rare cases in which this occurs.

In exploratory analyses, we will use logistic regression to model ventilator need as a function of treatment group and other baseline characteristics. Survival analysis methods will be used to analyze time to mechanical ventilation, with censoring at last follow-up for those not needing ventilation.

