Day 28 discharge will be trichotomized as death prior to day 28, discharge by day 28, hospitalized after day 28. Groups will be compared using Chi square test for independence.

Survival analysis methods will be used with death prior to discharge considered as a competing risk.

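### The safety population and the 60-day follow-up both start at Neoral, so Arm B has no stated start date, and section 11.5 does not say that adverse event rates will be compared, or even shown, by arm

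*Combined protocol and SAP*

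**What the plan says.** - **Safety population (11.4.1).** The definition reads: "All patients will be evaluable for toxicity from the time of their first treatment with Neoral and throughout the study period". It goes on to state that "patients will receive 7 days of Neoral and incidence of Neoral-associated toxicity events" will be assessed daily, together with all adverse events. No arm is distinguished.
- **Follow-up (6.4).** "Patients will be followed for 60 days after beginning the 7. day course of neoral or until death, whichever occurs first".
- **Treatment arms (6.1).** Arm A has 50 patients on Neoral. The Arm B entry for agent is "None*, N= 25 Patients", and the footnote to that table says placebo capsules were not feasible.
- **Safety analysis (11.5).** Adverse events and SAEs "will be summarized descriptively with frequencies and rates", and grade 3 or higher events get rates with 95% CIs. Neoral-associated toxicities are listed (renal, resistant hypertension, hepatic, CNS, superinfection). No arm, difference or test is named for any of these.
- **Other endpoints (11.5).** The same section does plan group comparisons elsewhere. Fisher's exact test will "compare rates of need for invasive mechanical ventilation". For day 28 discharge, "Groups will be compared using Chi square test for independence". Survival methods are also used to compare groups.
- **Collection.** Table 1 monitors adverse events continuously from consent and sets visits by study day, with no restriction by arm. Section 12 follows all adverse events and mortality to day 60.
- **Other analysis sets.** Section 11.4.2 analyses primary and secondary objectives in all randomised patients. Section 11.4.3 does so in randomised patients who complete 7 days of Neoral. Safety is secondary objective 1.2.1.

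**The concern.** A start date defined by an event that one arm never experiences does not define a start for that arm. Under the wording of 11.4.1 and 6.4, a third of the trial (25 of 75) has no point of entry to the safety population and no origin for the 60-day clock.

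Section 11.5 does not repair this, because it never says that rates are shown by arm. An analyst who follows the text literally would report a set of Neoral-arm rates and stop there.

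These patients are acutely ill. Table 3 assumes that 33% of controls (17 + 8 + 8) will be dead or on invasive ventilation at day 14, so renal, hepatic and infectious events may well occur without Neoral. An uncontrolled rate cannot separate drug from disease and co-treatment. The randomised control arm can supply that background rate, but the rules as written do not clearly require its use for objective 1.2.1.

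**Working it through.** **1. Setting the passages side by side**

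| Passage | Start or set | Does it place Arm B? |
|---|---|---|
| 11.4.1 | First Neoral treatment | Not if read literally |
| 6.4 | Start of the Neoral course | Not if read literally |
| Table 1 | Consent, then study days | Probably: no arm restriction, but Day 1 is not defined for Arm B |
| Section 12 | All events to day 60 | Probably: not tied to Neoral |
| 11.4.2 | All randomised | Yes, for secondary objectives |
| 11.4.3 | Completed 7 days of Neoral | Not if read literally |

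The first two rows fix who is evaluable for safety and from when. Table 1 and section 12 govern collection. The last two rows give different sets for the secondary objectives, and no clause says which set governs 1.2.1.

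**2. The plan's only numerical safety figures**

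These are the operating characteristics of the Table 4 boundary (11.6.2). An exact binomial recursion over n = 1 to 50 gives crossing probabilities of 4.8%, 39.2% and 86.4% at true rates of 20%, 30% and 40%. The plan states at most 5%, 40% and 86%, so its figures are reproduced. Table 4 ends at 50 patients, the size of Arm A, and nothing below changes it.

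**3. What a Neoral-only rate can and cannot show**

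The documents give no background toxicity rate, so every count here is assumed. The illustration uses grade 3 or higher targeted toxicities (renal, hypertension, liver), to which the 20% acceptable rate in 11.6.2 applies. Take 10/50 on Neoral.

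- Alone: 10/50 = 20%, exact (Clopper-Pearson) 95% CI 10.0 to 33.7%.
- With a control column, the difference is 10/50 minus x/25, with Newcombe 95% CIs:

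| Assumed control | Difference (points) | 95% CI |
|---|---|---|
| 0/25 (0%) | +20.0 | 4.1 to 33.0 |
| 3/25 (12%) | +8.0 | -12.0 to 23.2 |
| 5/25 (20%) | 0.0 | -21.0 to 17.1 |

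The Neoral-only line is identical in all three cases.

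**4. Precision of the contrast**

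With a common true rate p, the Wald half-width is 1.96 × √[p(1−p)(1/50 + 1/25)]:

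- p = 10%: 1.96 × √(0.09 × 0.06) = 14.4 points
- p = 20%: 1.96 × √(0.16 × 0.06) = 19.2 points
- p = 30%: 1.96 × √(0.21 × 0.06) = 22.0 points

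The power of a two-sided 5% Fisher test with 50 vs 25 patients is about 11% for 30% vs 20%, and 39% for 40% vs 20%. The contrast can serve as an estimate but not as a powered test.

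**5. Evenness of capture**

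A footnote to Table 1 suspends assessments between an early discharge (before 7 days) and the first outpatient visit. Table 3 (categories 1 + 2) assumes that 24 + 23 = 47% of controls are out of hospital at day 14, against 39 + 39 = 78%, 35 + 35 = 70% or 32 + 32 = 64% of CSA patients. If discharge timing does differ by arm, event capture may differ too.

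**The case against.** The strongest reply is that the protocol already covers Arm B. Section 11.4.1 opens by referring to all patients, Table 1 and section 12 carry no arm restriction, and 11.4.2 puts secondary objectives, safety among them, in all randomised patients. On this view the Neoral-anchored sentences are loose single-arm wording. Much of this stands. A reader might infer from 11.4.1 and 6.4 that Arm B events will not be collected, or cannot be analysed. The documents do not support that.

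The reply does not close the gap. The sentence that begins with all patients dates their evaluability from a treatment that a third of them never receive. Collection rules do not define an analysis set, and 11.4.2 competes with 11.4.1 and 11.4.3 without a rule of precedence. Nothing states that adverse event rates are shown by arm.

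A second reply is that descriptive safety reporting is acceptable in a phase IIa trial of 75 patients. That is right, and the power figures confirm that a hypothesis test would add little. A risk difference with its interval is still descriptive, and it uses the comparator that randomisation provides.

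A third is that the illustrated differences follow from the counts chosen. That is also right. They show why a control column is informative in general. They do not measure what this trial would lose.

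**Conclusion.** The point holds as a faulty population definition and an unspecified safety comparison, and should be corrected before analysis. It is not a finding of missing data: Arm B events are probably collected to day 60, although no passage says so outright for both arms.

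No sample size, power or boundary figure is affected. The consequence is that objective 1.2.1 could be answered from uncontrolled Neoral rates. Its size cannot be derived from the documents. Under the assumed counts, one Neoral-only result of 20% (10 to 34%) is compatible with a clear excess over control or with none. The textual part rests on the literal wording of 11.4.1, 6.4 and 11.5. The numerical part rests wholly on assumed event rates.

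**What to change.** 1. **11.4.1 and 6.4.** Define the safety population as all randomised patients in both arms. Use one start that applies identically to each arm, namely randomisation, and run through day 60. State that this set governs objective 1.2.1.
2. **11.5.** Report grade 3 or higher events, SAEs and each Neoral-associated toxicity by randomised arm, with the risk difference and 95% CI. Label these as estimation only and open to open-label reporting bias.
3. **Supplementary.** Give an as-treated table (at least one Neoral dose). Flag Arm A patients who were never dosed, including any registration cancelled under 4.2. Keep the Neoral-only count for the Table 4 boundary.

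The main table should not start at randomisation and then restrict the Neoral column to dosed patients. Section 4.2 allows up to 2 days between registration and treatment, so that rule would drop pre-dose events in one arm only. A split into inpatient and post-discharge events is best omitted, or labelled descriptive and not a randomised comparison, because discharge occurs after randomisation and Table 3 expects it to differ by arm.

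**Cost.** Wording in three sections, plus a control column and a difference column in the adverse event tables. Probably no new data items are needed, but Arm B follow-up to day 60 should be confirmed. The downsides are wide intervals (half-widths of about 14 to 22 points for assumed true rates of 10 to 30%), open-label reporting bias, and possibly uneven event capture after early discharge.

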11.4.2 Intent to treat (ITT) population

All randomized patients in the study will be assessed for response to treatment, even if there are major protocol treatment deviations. Each patient will be assigned one of the WHO COVID scale categories outlined in **Table 2**. Primary and secondary objectives will be analyzed.

11.4.3 Modified intent to treat (MITT) population

Primary and secondary objectives will be analyzed in all randomized patients who complete 7 days of Neoral.

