4.3 Randomization

Patients will be randomized in a 2:1 ratio to receive either CSA or placebo (no CSA). Randomization will be open-label, using the permuted block method and will be stratified by age (<60 or >60 years), WHO severity (4 vs. 5), presence or absence of comorbidities (at least one of the following – hypertension, coronary artery disease, congestive heart failure, or diabetes). Randomization will be performed centrally at the Baylor College of Medicine by the Project Manager.

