6.3 Duration of Therapy

In the absence of treatment delays due to adverse event(s), treatment may continue for 7 days or until one of the following criteria applies:

- Intercurrent illness that prevents further administration of treatment
- Unacceptable adverse event(s)
- Patient decides to withdraw from the study
- General or specific changes in the patient's condition render the patient unacceptable for further treatment in the judgment of the investigator
- Patient non-compliance
- Termination of the study by sponsor
- The drug manufacturer can no longer provide the study agent

The reason(s) for protocol therapy discontinuation, the reason(s) for study removal, and the corresponding dates must be documented in the Case Report Form (CRF).

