8. STUDY CALENDAR

Table 1 Schedule of Study Events (Part 1)

Visit	Screening	Baseline	Treatment ¹							Follow-up ²		
	1	2	3	4	5	6	7	8	9	10		
Study Day	-21 to -1	-2 to 0	1	2	3	4	5	6	7	8	9	10
Written Informed Consent	X											
Assign Screening Number	X											
Complete Medical History	X											
Demographics	X											
Inclusion/Exclusion Criteria Review	X											
WHO COVID-19 Severity Scale	X	X	X	X	X	X	X	X	X	X	X	X
Assign Enrollment Number		X										
Complete Physical Examination	X	X	X	X	X	X	X	X	X	X	X	X
Vital Signs (BP, HR, RR, Temp, SpO ₂)	X	X	X	X	X	X	X	X	X	X	X	X
FIO ₂ Assessment	X	X	X	X	X	X	X	X	X	X	X	X
Pregnancy Test for Female Patients	X											
Cyclosporine Administration			X	X	X	X	X	X	X			
12-Lead ECG	X								X			X
Chest X-ray	X								X			X
BMP	X	X	X	X	X	X	X	X	X	X	X	X
LFTs	X	X	X	X	X	X	X	X	X	X	X	X
CBC	X	X	X	X	X	X	X	X	X	X	X	X
ANC	X	X	X	X	X	X	X	X	X	X	X	X
Absolute Lymphocyte Count	X	X	X	X	X	X	X	X	X	X	X	X
Total Cholesterol	X	X										
Ferritin	X	X	X	X	X	X	X	X	X	X	X	X
D-Dimer	X	X	X	X	X	X	X	X	X	X	X	X
CRP	X	X	X	X	X	X	X	X	X	X	X	X
LDH	X	X	X	X	X	X	X	X	X	X	X	X
Magnesium	X	X	X	X	X	X	X	X	X	X	X	X
Phosphorus	X	X	X	X	X	X	X	X	X	X	X	X
PT/PTT	X	X							X			
SARS-CoV-2 PCR	X											
AE Assessment	Continuous Monitoring from Signing of the Informed Consent-----►											
Concomitant Medications/Therapies	Continuous Monitoring from Signing of the Informed Consent-----►											

ANC =Absolute neutrophil count; BMP =basic metabolic panel; BP = blood pressure; CBC = complete blood count; CRP =c-reactive protein; ECG = Electrocardiogram; FIO₂ = oxygen requirement; HR = heart rate; LDH = lactate dehydrogenase; LFTs = liver function tests; PT = prothrombin time; PTT = partial thromboplastin time; RR = respiratory rate; SpO₂ = oxygen saturation; WHO = World Health Organization.

¹Treatment assessments will be performed every 24±6 hours. Treatment is Neoral for 7 days and will discontinued on the day of discharge if the patient is discharged before the 7d course is completed. If the patient is discharged before 7 days, the patient will not undergo any assessments until the first outpatient visit.

²Follow up will be performed every 24±6 hours while inpatient. Once patient is discharged, follow up will be at days 14±3 days, 28±3 days, and 60±3 days either by in person clinic visit or telemedicine visit.

Table 1 Schedule of Study Events (Part 2)

Visit	Follow-up ²							
	11	12	13	14	15-27	28	60	
Study Day	11	12	13	14	15-27	28	60	

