11.2 Sample Size /Justification

We expect to see higher grades of WHO COVID ordinal clinical scale in control group compared to the CSA treatment group, and propose to use a 1 to 2 randomization in favor of CSA group.

The total sample size of 75 evaluable participants will provide 81% power to reject the null hypothesis that the grade in control group is less than or equal to the CSA group with a 10% one-sided significance level when the true effect size, as measured by the probability that

Control grade is greater than CSA grade, is 0.65 or greater. Sample size and/or power for the various scenarios were calculated using nQuery 8 (StatSols Version 8.5.2.0).

The following provides the rationale for the alternate hypothesis effect size. We have assumed that all participants will be starting in category 4. Based on review of hospital data, about one third of such patients end-up in the ICU and about half of those patients will die. Of the two thirds that do not go to the ICU, most will be discharged in 2 weeks or less. We have therefore hypothesized that at 2 weeks following enrollment, the control group will be distributed as shown in the table 3.

We have hypothesized several scenarios to estimate the sample size needed to detect a CSA effect with reasonable power. We expect the effect of CSA will be to reduce ICU admissions, or to shorten time in the ICU and reduce deaths, so that the fraction in categories 6, 7, and 8 on Day 14 will be reduced and less ill patients will go home earlier, increasing the fraction of 1 and 2's on day 14.

Since the outcome is ordinal, a Wilcoxon rank sum test is used to control (no CSA) and CSA on day 14. The one-tailed null hypothesis is that the distribution of WHO scores is the same in two groups or worse in CSA, and the alternative is that the distribution of WHO scores in the CSA group is shifted lower. The effect size ($P_1 = \Pr(\text{Control} > \text{CSA})$) is the probability that a randomly selected observation from the control group has a score greater than one from CSA group. The null value for P_1 is 0.5 and the closer P_1 to 1, the bigger the effect.

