11.4.4 Per-protocol analysis population

Sub-analyses may then be performed on the basis of a subset of ITT population, excluding those for whom major protocol deviations have been identified (e.g., early death due to other reasons, early discontinuation of treatment, major protocol violations, etc.). However, these sub-analyses

may not serve as the basis for drawing conclusions concerning treatment efficacy, and the reasons for excluding patients from the analysis should be clearly reported.

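### The modified ITT set requires completing Neoral, so it contains no controls; keeping the controls anyway still selects one arm on post-randomisation outcome

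*Combined protocol and SAP*

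**What the plan says.** Section 11.4.3 defines the modified intent-to-treat set in one sentence: "Primary and secondary objectives will be analyzed in all randomized patients who complete 7 days of Neoral". It has no clause for the control arm.

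Section 6.1 lists the Arm B agent as "None*, N= 25 Patients", and its footnote explains that "generation of placebo capsules is not feasible for the timing of this study". Footnote 1 to Table 1 (Section 8) says of Neoral that it "will discontinued on the day of discharge if the patient is discharged before the 7d course is completed". Under Section 6.3, "treatment may continue for 7 days or until one of the following criteria applies"; the criteria include intercurrent illness, unacceptable adverse events, a change in condition as judged by the investigator, non-compliance and withdrawal.

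Section 11.4.2 separately defines an ITT set of all randomised patients and also assigns the primary and secondary objectives to it. Section 11.1 specifies a between-group Wilcoxon test on day 14 and names no analysis set. Section 11.4.4 says that per-protocol sub-analyses "may not serve as the basis for drawing conclusions concerning treatment efficacy". Section 11.4.3 carries no such restriction.

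**The concern.** Membership depends on finishing a drug that only one arm is given. Read literally, the set is a single-arm group of completers, and the planned two-group test on the primary endpoint does not exist.

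The generous reading keeps every control and applies the completion rule to Neoral patients only. That arm is then chosen on events after randomisation, with no matching choice among controls. Removing early deaths flatters Neoral. Removing early discharges penalises it, and Section 11.2 expects Neoral to send less ill patients home sooner, so the more the drug works in that way, the more of its successes are discarded. A planned analysis of the primary endpoint, under a name that suggests randomisation has been respected, could show a benefit that is not there or hide one that is.

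**Working it through.** **1. Who can be in the set**

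- Control patients: none, because no Neoral is given.
- Neoral patients who die before day 7: cannot complete.
- Neoral patients discharged before day 7: cannot complete, by footnote 1 to Table 1.
- Neoral patients who worsen: not excluded automatically. Under 6.3 this turns on the investigator's judgement or on illness that prevents dosing.

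Read literally, the comparison has 0 controls. This step needs no assumption.

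**2. Reproducing the plan's power**

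Table 3 (Section 11.2) gives, for scores 8 down to 1, control 17/8/8/5/5/10/24/23% and Scenario 1 8/4/4/2/2/2/39/39%.

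P1 = Pr(control > CSA) + ½ Pr(tie) = 0.5466 + ½ × 0.2073 = 0.650, as stated in the plan.

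With 25 controls, 50 Neoral patients and a one-sided 10% Wilcoxon test (200,000 simulated trials), power is 81.1% without a tie correction and 82.8% with it. The plan states 81%. With nobody excluded, type I error is 10.1%. The tie-corrected test is used below, so the baseline power is 83%.

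**3. Completion rule applied to Neoral only, all 25 controls kept**

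Let *d* be the share of Neoral day-14 deaths that occur before completion, and *e* the share of Neoral patients scoring 1 or 2 on day 14 who were discharged before completion. The documents give neither. The nearest statement is "Of the two thirds that do not go to the ICU, most will be discharged in 2 weeks or less" (Section 11.2), which says nothing about day 7. Both are therefore assumptions, varied from 0 to 75%.

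The chance that a random control scores worse than a Neoral patient with score *k*, counting ties as half, is:

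- *k* = 8: ½ × 0.17 = 0.085
- *k* = 2: 0.53 + ½ × 0.24 = 0.65
- *k* = 1: 0.77 + ½ × 0.23 = 0.885

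No true effect (Neoral follows the control column):

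P1 = [0.5 − 0.17 × 0.085*d* − (0.24 × 0.65 + 0.23 × 0.885)*e*] / [1 − 0.17*d* − 0.47*e*] = [0.5 − 0.01445*d* − 0.35955*e*] / [1 − 0.17*d* − 0.47*e*]

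Scenario 1:

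P1 = [0.65025 − 0.0068*d* − 0.59865*e*] / [1 − 0.08*d* − 0.78*e*]

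Examples with no true effect:

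- *d* = 0.5, *e* = 0: 0.492775 / 0.915 = 0.539
- *d* = 0, *e* = 0.5: 0.320225 / 0.765 = 0.419

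An unbiased comparison would give 0.500.

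**4. Simulated consequences**

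False benefit is rejection in favour of Neoral when there is no effect. False harm is rejection in the opposite one-sided 10% test.

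| *d* | *e* | Neoral kept of 50 (no effect) | P1 (no effect) | False benefit | False harm | P1 (Scenario 1) | Power (Scenario 1) |
|---|---|---|---|---|---|---|---|
| 0 | 0 | 50.0 | 0.500 | 10.1% | 10.1% | 0.650 | 82.7% |
| 50% | 0 | 45.8 | 0.539 | 23.5% | 3.7% | 0.674 | 90.0% |
| 0 | 50% | 38.2 | 0.419 | 0.9% | 43.3% | 0.575 | 38.6% |
| 25% | 25% | 42.0 | 0.484 | 6.9% | 14.8% | 0.636 | 73.6% |
| 50% | 25% | 39.9 | 0.505 | 11.7% | 9.3% | 0.650 | about 80% |
| 25% | 50% | 36.1 | 0.438 | 1.9% | 32.9% | 0.592 | about 47% |
| 50% | 50% | 34.0 | 0.460 | 3.9% | 22.8% | 0.610 | 55.8% |

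The two power entries marked *about* come from a smaller run of 20,000 trials; the others use 200,000. Over the whole 0 to 75% grid with no true effect, P1 runs from 0.356 to 0.561 and false benefit from 0.1% to 33.9%.

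**The case against.** The sound analysis is already planned. Section 11.4.2 keeps every randomised patient whatever the deviations, the sample size uses the full 25:50, and nothing makes the modified set primary. Section 11.4.4 speaks of subsets of the ITT population that exclude early discontinuation, which in substance describes a completer set. The most striking figures also come from corner cells in which only deaths or only discharges occur early; with both, the biases offset, and at 50%/25% they almost vanish.

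Much of this stands. The ITT comparison and the 81% power are unaffected. The sign of the bias is unknown and its size may be small, so the corner cells are bounds rather than forecasts. The simulation also leaves out stops for adverse events, non-compliance and withdrawal.

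It does not remove the fault. No section ranks ITT above the modified set, and Section 11.2 refers to evaluable participants without defining them. The 11.4.4 restriction sits under the per-protocol heading, where analyses are optional, while the modified analysis is stated as definite. Near-cancellation would be an accident of timing. The absence of controls depends on none of these assumptions.

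**Conclusion.** The concern holds. As written, the modified ITT analysis of the primary endpoint has no comparator. Repaired in the obvious way, it is still selected in one arm on death and on early discharge. The absence of controls and the one-sided selection follow from the text alone. The size of the bias rests on assumed shares leaving before day 7, on the Table 3 distributions, and on modelling only deaths and discharges as reasons for not completing. The damage is confined to this analysis and to the failure to name the primary set.

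**What to change.** State in Section 11.1 that the primary analysis uses the ITT set of 11.4.2. Then do one of the following with 11.4.3:

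- delete it;
- redefine it by criteria that apply identically to both arms and do not depend on completing treatment, for example all randomised patients with confirmed eligibility;
- keep it as an exploratory completer analysis, say in advance how controls enter, and give it the same bar on efficacy conclusions as 11.4.4.

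This should be settled before outcome data are seen, since deciding afterwards how controls enter would be a data-dependent choice. The cost is protocol and SAP wording only: no added patients and no added data collection.
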